8.2.1 SAFETY POPULATION

The **Safety** Population includes eyes with attempted study lens (HMIOL) implantation, (successful or aborted after contact with the eye). The intraoperative and postoperative AEs and DDs will be summarized based on the safety population.

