4.5 SUBJECT DISCONTINUATION

A subject **MUST** be discontinued prior to the final study visit for any of the following reasons:

- Death
- Subject is enrolled and scheduled for surgery but is not implanted with an HMIOL at Day 0 (Operative Visit – Primary Cataract Extraction)
- Surgical complication(s) unrelated to the investigational device preventing the implantation of the HMIOL (i.e. capsulorhexis tear, zonular rupture, evident zonular weakness or dehiscence, posterior capsular rupture, vitreous loss, posterior capsular plaque, significant detached Descemet's membrane, significant anterior chamber bleeding, iris incarceration or damage, corneal endothelial touch, unsuccessful/incomplete phacoemulsification, haptic and/or optic damage/haptic amputation)
- Explantation of the HMIOL System

If the study lens is explanted, one postoperative visit should be completed to record best-corrected distance visual acuity (BCDVA) before the subject is discontinued.

Subjects who withdraw from the study will be asked to complete procedures outlined in the 12 Month Visit (if withdrawn prior to that visit). Subjects who are terminated due to an AE will be followed, if possible, at least until resolution or stabilization of the AE. Subject withdrawals will be documented clearly on the source document and applicable eCRF.

Prior to discontinuing a subject, every effort should be made to contact the subject, schedule a final study visit, and obtain as much follow-up data as possible. Adverse events will be followed as described in Section 6.3.4. Discontinued subjects should be followed outside of the study protocol according to the Investigator's normal postoperative standard of care.

A Study Exit eCRF must be completed for all subjects who discontinue from the clinical investigation.

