5.5 OTHER MATERIALS

Additional materials can be provided to sites for the duration of the study on an as-needed basis and may include:

- ETDRS light box, glare source, and charts to perform the standardized VA assessments described in the Manual of Procedures
- Medical injectors (for study lens injection only)
- IOL micro-incision cutter and forceps
- 40 cm measuring tool to perform near vision testing
- Konan Specular Microscope
- Pentacam Anterior Segment Imaging System

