6.1.4 DEVICE DEFICIENCIES (DD)

A Device Deficiency (DD) is a failure of the device to meet its performance specifications or expectations, or otherwise not perform as intended. This can include either a malfunction or damage to the device or any part thereof, regardless of the source of malfunction or damage, including user error, and regardless of the presence of injury (or lack thereof) to subject, user, or bystander.

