6.3.3 REPORTING OF COMPLAINTS FOR ANCILLARY MARKETED PRODUCTS

Any complaints, malfunctions or similar events related to ancillary marketed products used in this study should be reported by the Investigators in accordance with the reference information provided on the associated commercial packaging.

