8.3.1 SAFETY OUTCOMES

8.3.1.1 ADVERSE EVENTS AND DEVICE DEFICIENCIES

Adverse events and device deficiencies will be summarized at each study visit based on the safety population for Cohort 1 and Cohort 2. The number and percentage of eyes reported with the ISO specified 12-month cumulative and persistent adverse events will be calculated for Cohort 1 and Cohort 2 separately. Additionally the events will be summarized for the HMIOL cohort (12-months after primary cataract surgery for Cohort 1 and 12-month after HMIOL optic exchange for Cohort 2). The corresponding one-sided lower 95% confidence limit will be calculated based on the binomial distribution and compared to the ISO SPE rate. If the one-sided lower 95% confidence limit is smaller than the SPE rate specified by ISO, then the null hypothesis of event rate of less than the SPE rate will not be rejected.

[REDACTED]

The ISO cumulative and persistent adverse events will also be provided for the fellow eye cohort and numerically compared to those of HMIOL eye cohort.

Additionally, the number and percentage of eyes reported with HMIOL-related adverse events during the study will be summarized for HMIOL Cohort 1, HMIOL Cohort 2, and HMIOL-eye Cohort. The two-sided 90% confidence interval of the percentage will also be provided.

8.3.1.2 [REDACTED]

[REDACTED]

[REDACTED]

[REDACTED]

[REDACTED]

[REDACTED]

[REDACTED]

[REDACTED]

[REDACTED]

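### Device deficiencies that end a case before any study lens touches the eye are recorded but fall outside the planned deficiency summary

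*Protocol*

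**What the plan says.** Protocol 8.2.1 builds the Safety Population from eyes in which HMIOL implantation was attempted and was "successful or aborted after contact with the eye". It then sets the scope of the tables: "The intraoperative and postoperative AEs and DDs will be summarized based on the safety population". Protocol 8.3.1.1 repeats this and adds the layout: "Adverse events and device deficiencies will be summarized at each study visit based on the safety population for Cohort 1 and Cohort 2". Section 8.3 adds a combined column, which is the sum of those two cohorts. SAP section 4 defines both cohorts, and the All HMIOL Eyes cohort, as eyes implanted with the device.

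The definition of a DD is wider. Section 6.1.4 covers malfunction of or damage to any part of the device, "regardless of the source of malfunction or damage, including user error, and regardless of the presence of injury". Contact with the eye is not a condition.

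Section 4.5 lists the subjects who must be discontinued, among them: "Subject is enrolled and scheduled for surgery but is not implanted with an HMIOL at Day 0". Section 2.0 makes feasibility of HMIOL implantation and assembly the primary objective.

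**The concern.** Contact with the eye is a sensible entry condition for adverse events, because the question there is what happened to an exposed patient. It is a poor condition for device performance. A base or optic found defective, or damaged during preparation, is a DD under 6.1.4 whether or not it reached the eye. If the case then ends with no HMIOL used, the eye is outside the Safety Population and the DD is outside the summary.

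Such an event bears directly on whether the lens can be implanted and assembled. The protocol says its analyses are meant to inform a later confirmatory study, so a summary without these events would give that study's planners too favourable a picture. Section 4.5 itself lists lens damage among the complications that may prevent implantation, although it does not say how often this is expected or whether it would occur before contact.

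**Working it through.** The documents give no expected number of DDs, no DD rate and no number of attempts stopped before contact, so there is no planned figure to reproduce. The check has two parts.

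**Tracing the rule.** For each kind of DD, the question is whether the eye is in the Safety Population (8.2.1) and whether it has a column (8.3.1.1, with SAP section 4).

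| Situation | In Safety Population | Has a cohort column |
|---|---|---|
| DD before contact, replacement HMIOL implanted | yes | yes |
| DD at optic exchange, even if the exchange is abandoned | yes, already implanted | yes; 3.3.4 returns the subject to Cohort 1 |
| DD after contact, implantation aborted | yes | no |
| DD before contact, no HMIOL then touches the eye | no | no |

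Only the last row drops out of the population. The third row stays in the population but has nowhere to appear in the layout.

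**Size.** Let N be the eyes in the Safety Population, m those with a DD, and k the eyes with a DD before contact and no HMIOL used. The planned proportion is m/N. Adding the lost eyes gives (m + k)/(N + k). The difference is

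(m + k)/(N + k) − m/N = k(N − m) / [N(N + k)],

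which is never negative. With m = 0 and k = 1 it is 1/101 = 0.99 percentage points at N = 100 and 1/201 = 0.50 at N = 200.

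N = 100 and 200 are the ends of the planned range of implanted eyes in the synopsis. The values of m and k are assumptions. Upper limits are exact one-sided 95%: 1 − 0.05^(1/n) for zero events, otherwise the 0.95 quantile of Beta(x + 1, n − x).

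| N | m | k | Planned summary (upper limit) | With lost eyes (upper limit) |
|---|---|---|---|---|
| 100 | 0 | 1 | 0/100 = 0% (2.95%) | 1/101 = 0.99% (4.61%) |
| 100 | 0 | 3 | 0/100 = 0% (2.95%) | 3/103 = 2.91% (7.36%) |
| 100 | 0 | 5 | 0/100 = 0% (2.95%) | 5/105 = 4.76% (9.75%) |
| 100 | 2 | 3 | 2/100 = 2.00% (6.16%) | 5/103 = 4.85% (9.94%) |
| 200 | 0 | 1 | 0/200 = 0% (1.49%) | 1/201 = 0.50% (2.34%) |
| 200 | 0 | 3 | 0/200 = 0% (1.49%) | 3/203 = 1.48% (3.78%) |
| 200 | 0 | 5 | 0/200 = 0% (1.49%) | 5/205 = 2.44% (5.06%) |
| 200 | 2 | 3 | 2/200 = 1.00% (3.11%) | 5/203 = 2.46% (5.11%) |

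With k = 0 nothing changes. The zero-event limits here differ from the 0.0362 and 0.0183 in the synopsis. Those equal 1 − 0.025^(1/n), which is a one-sided 97.5% limit.

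**The case against.** The strongest reply is that the data are not lost. Section 3.3.2 requires DDs around the Day 0 surgery to be recorded, 6.3.1 requires every DD to reach the sponsor within 24 hours, 6.4 has each reviewed on receipt, and 5.4 logs defective devices. A reader might infer that these DDs go unseen. They do not; only the scope of the reported summary is at issue. That part of the reply stands. It does not put the events into the table, and no readable section summarises DDs by attempt or by lens opened. Section 8.2 promises a summary of screen-failure reasons, but a DD is not among the named intra-operative exclusion criteria in 3.2.3.

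Second, the trigger is narrow, since the case must end with no HMIOL touching the eye. That also stands, so it cannot be said that the DD frequency will be too low, only that it may be.

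Third, no readable endpoint is a DD rate, and 8.3.1.1 attaches no confidence interval to DDs. Section 8.0 calls for counts and percentages of categorical outcomes, so a DD percentage is a fair reading, but the limits above are illustrative. Some safety endpoints are redacted.

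Fourth, SAP section 2 lets the SAP supersede the protocol's analyses, and the SAP's Safety Population definition is not in the supplied text. It might be wider. The readable part of SAP section 5.5 describes adverse event tables and does not mention DDs.

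**Conclusion.** The point holds in a limited form. As the protocol is written, a DD that stops the case before any HMIOL touches the eye is left out of the planned summary, and an eye aborted after contact has no column. The direction is certain, because omitting such eyes can only lower the apparent frequency. The size is not known: about 1 percentage point per eye at 100 eyes and 0.5 at 200, and nil if no such case occurs. The conclusion rests on the protocol text and assumes that the SAP definition does not widen the population.

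Three stronger readings are not supported:

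- A reader might take the 105 subjects in section 4.7.1 as the planned number of implantations. That figure is an enrolment minimum tied to possible early termination; the plan is for 100 to 200 implanted eyes.
- A reader might conclude that DDs must be counted per component. That is a possible preference, but the defect does not depend on it, and the records listed in 5.4 include no count of components opened.
- A reader might add that section 6.3.3, which directs complaints about ancillary marketed products to the route given on their packaging, hides delivery failures. That depends on which supplied instruments are marketed products, and it concerns reporting rather than the analysis set.

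**What to change.** In Protocol 8.2.1 and 8.3.1.1, keep adverse events on the Safety Population. Summarise DDs over all eyes taken to surgery for which an HMIOL was opened or prepared, whether or not it touched the eye. Add a column for non-implanted eyes, which also gives a place to eyes aborted after contact, and a separate line for DDs that ended the implantation or the exchange. Make the same change in the SAP if its Safety Population definition has the same limit, and name the DD table there.

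The numerator needs no new data, since every DD is already reported. The denominator needs a way to identify eyes for which a lens was opened or prepared but not used. Neither the surgical details in 3.3.2 nor the records in 5.4 list this as an item, so it should be confirmed from the surgical record or added as one yes/no field. Eyes where a lens was opened and the case stopped for another reason would enter the denominator only. Otherwise the cost is a wording change and one more table, and the DD figure may look slightly less favourable.

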8.2.2 IMPLANTED-EYE POPULATION

The **Implanted-Eye** Population consists of eyes with successful HMIOL implantations during surgeries. Since it is important to evaluate HMIOL's effect on the study [REDACTED] slit lamp examination, intraoperative pressure (IOP), and dilated fundus examination (DFE) will be based on the implanted-eye population.

Additionally, the UCDVA, BCDVA, mesopic BCDVA (mBCDVA) with and without glare, MRSE, absolute EPR, and [REDACTED] will be evaluated based on the implanted-eye population.

8.2.3 PER PROTOCOL POPULATION

The **Per Protocol (PP)** Population contains eyes with successful HMIOL implantations during surgeries and do not have major protocol deviation (such as improperly enrolled in the study or lens power calculation errors) and will be considered the primary population for effectiveness outcomes. The effectiveness outcomes (UCDVA, BCDVA, mBCDVA with and without glare, MRSE, and absolute EPR) will be evaluated based on the per protocol population.

The protocol deviations will be determined reviewed by ClarVista clinical personnel prior to analysis.

8.2.4 BEST-CASE POPULATION

The **Best Case** population is the PP population with all of the following characteristics:

- No clinically significant preoperative ocular pathology in the study eye, including any of the following present at the preoperative visit
 - Pseudoexfoliation
 - Glaucoma
 - Uveitis
 - Retinal detachment

CLARVISTA MEDICAL

PROTOCOL CP-00001 Rev.05

- Diabetic retinopathy
 - Macular degeneration
 - Amblyopia
 - Others as specified by unmasked sponsor clinical personnel after a review of the adverse events present at the preoperative visit
- No macular degeneration detected at any time in the study eye
 - No previous surgery for the correction of refractive errors in the study eye

The purpose of the Best Case population is to evaluate BCDVA as described in ISO 11979-7:2014.

8.3 STATISTICAL METHODS

The data analyses will be based on the analysis populations described above. No imputation for missing data will be performed. The statistical summaries will be prepared for HMIOL Cohort 1, HMIOL Cohort 2, and HMIOL eye Cohort (Cohort 1 + Cohort 2). For some selected outcomes, the summaries will be prepared for the fellow eye cohort.

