	
Cohort 1. Subjects who opt for an optic exchange procedure will be entered into Cohort 2.
 
All fellow eyes will receive a commercially approved IOL and standard of care (SOC) follow-up for 12 Months.
 
For purposes of accountability and analysis, there will be the following Cohorts:
 
 • All HMIOL Eyes Cohort (All eyes receiving study device) • HMIOL Cohort 1 (HMIOL eyes without optic exchange) • HMIOL Cohort 2 (HMIOL eyes with optic exchange) • Fellow Eyes Cohort 
Post-Operative Visits
 
All HMIOL Eyes Cohort
 
 • 1 Day, 1 Week, 1 Month, 3 Month following primary cataract extraction 
HMIOL Cohort 1 (HMIOL subjects without optic exchange procedure)
 
 • 6 Month, and 12 Month Visits following primary cataract extraction 
HMIOL Cohort 2 (HMIOL subjects undergoing optic exchange)
 
 • Optic exchange decision and assignment to Cohort 2 at 3 Month Visit as deemed necessary by Investigator and Subject • 1 Day, 1 Week, 1 Month, 3 Month, 6 Month, and 12 Month Visits following optic exchange 

Study Endpoints
	
The safety and effectiveness of HMIOL for the treatment of aphakia in subjects following cataract extraction will be characterized along with the safety and effectiveness of the HMIOL optic exchange procedure in the subgroup of study subjects with optic exchange.
 
Safety Endpoints:
 
All HMIOL Eyes Cohort:
 
 • 

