3.0 STUDY DESIGN

3.1 DESCRIPTION OF THE STUDY

This is a prospective, multi-center, feasibility study being conducted at up to 7 investigative sites. All sites will have Institutional Review Board (IRB) or Ethics Committee (EC) review and approval prior to recruiting potential subjects. Up to 200 eligible subjects with bilateral cataracts will undergo cataract extraction in each eye during participation. Within approximately one to four weeks post-implantation of the HMIOL, the fellow eye (FE) will be implanted with a commercially available IOL.

At the 3 Month Visit (post-primary cataract extraction), subjects with satisfactory outcomes, or those opting not to pursue an optic exchange, will be entered into Cohort 1.

Subjects who opt for an HMIOL optic exchange in their primary eye will be entered into Cohort 2.

[figure not shown]

FIGURE 2 - COHORT DESIGNATION

All subjects enrolled in this study will be evaluated for 12 months following either primary cataract extraction or optic exchange, whichever is later (see Appendix A – Schedule of Assessments).

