 15. Taking systemic medications that, in the opinion of the investigator, may confound the outcome or increase the risk to the subject (e.g. Tamsulosin Hydrochloride – Flomax) or other medications including anticholinergics, alpha adrenergic blocking agents with similar side effects (e.g. small pupil/floppy iris syndrome)
- 3.2.3 EXCLUSION CRITERIA DURING SURGERY
1. Vitreous loss prior to use of the investigational device
 2. Positive posterior pressure preventing safe implantation of the lens system
 3. Anterior chamber hyphema preventing visualization of implantation
 4. Any zonular or capsular rupture or capsular bag instability

CLARVISTA MEDICAL

PROTOCOL CP-00001 Rev.05

5. Intraoperative miosis preventing visualization of fixation features
6. Need for concomitant procedures (e.g. glaucoma surgery, LRI, RK, LASIK, etc.)
7. Subject who, in the clinical judgment of the investigator, is not suitable for participation in the study for another clinical reason, as documented by the investigator

3.2.4 EXCLUSION CRITERIA – 3 MONTHS POST-PRIMARY CATARACT EXTRACTION (AFFECTING ELIGIBILITY FOR HMIOL OPTIC EXCHANGE)

1. Any clinical finding or intraocular complication during primary cataract extraction that (in the judgment of the Investigator) is likely to increase complications with optic exchange procedure or present undue risk to the subject (e.g. unexplained endothelial cell loss, post-primary cataract extraction macular edema, persistent ocular inflammation, etc.)
2. Presence of YAG Capsulotomy in the primary (HMIOL) eye

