At the 3 month visit, an overall assessment of a subject's visual function will be performed by the physician. If the physician's assessment results in an opportunity for improved visual function through optic exchange in the test eye, the subject will be offered that opportunity. The Investigator and the Subject will decide if an optic exchange is appropriate.

The decision will be documented and the prospective Cohort indicated.

- If the subject has an acceptable outcome or it is otherwise decided an optic exchange will not take place, the subject will be entered into Cohort 1 and be followed at the 6 and 12 Month Visits prior to study completion. If the subject desires an exchange, however it is decided they cannot have one based on exclusion criteria (Section 3.2.4), the subject will remain in Cohort 1 and can utilize spectacles to correct RRE for the remainder of study participation. The investigator and subject can decide on further treatment per the Investigator's standard of care, following study participation.
- If it is decided an HMIOL optic exchange is desired, the appropriate pre-operative measurements will be obtained, 3 Month Visit assessments completed per Appendix A – Table 1, and HMIOL calculations and optic ordered. Finally, the subject will be scheduled for the procedure and entered into Cohort 2 (finalized after successful completion of optic exchange). If for any reason the optic exchange procedure does not take place, the subject will default back to Cohort 1.

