Several cohorts of subjects are specified to help characterize the clinical significance of the study outcomes in eyes with and without optic exchange. These cohorts are defined as follows:

All HMIOL Eyes Cohort: Defined as all study eyes implanted with the study device. Analysis of follow-up visits for this cohort definition is restricted to 1 Day, 1 Week, 1 Month, and 3 Months following primary cataract extraction (PCE).

Cohort 1: Defined as the subset of study eyes implanted with the study device without a subsequent optic exchange procedure. Analysis of follow-up visits for this cohort definition is restricted to 1 Day, 1 Week and 1, 3, 6 and 12 Months following primary cataract extraction.

Cohort 2: Defined as the subset of study eyes implanted with the study device with a subsequent optic exchange procedure. Analysis of follow-up visits for this cohort will cover two time periods:

- Pre-Optic Exchange, comprising 1 Day, 1 Week, 1 Month, and 3 Months following primary cataract extraction, prior to the optic exchange visit.
- Post-Optic Exchange, comprising 1 Day, 1 Week, 1 Month, 3 Months, 6 Months, and 12 Months following optic exchange. The baseline for the post-optic exchange visits is the 3 Month pre-optic exchange visit.

Fellow Eyes Cohort: Defined as the contralateral eyes not implanted with the study device. Analysis of follow-up visits for this cohort definition is restricted to 1 Day, 1 Week, 1 Month, 3 Months, 6 Months, and 12 Months following primary cataract extraction.

Separate analyses are planned for each cohort.

Protocol CP-00001

ClarVista Medical, Inc.

5. Statistical Analyses

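### Eyes that fail or exit before the optic exchange count against Cohort 1 and never Cohort 2, and the SAP has no all-eyes cohort at one year for its SPE comparison

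*Protocol*

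**What the plan says.** **Cohort definitions for analysis.** The protocol synopsis lists "All HMIOL Eyes Cohort (All eyes receiving study device") and "HMIOL Cohort 1 (HMIOL eyes without optic exchange"). SAP 4 agrees in substance. For the All HMIOL Eyes Cohort it says "Defined as all study eyes implanted with the study device", and for Cohort 1 "Defined as the subset of study eyes implanted with the study device without a subsequent optic exchange procedure". Cohort 2 is the eyes that had the exchange.

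**Follow-up windows.** SAP 4 analyses Cohort 1 from Day 1 through 12 months and Cohort 2 both before and after the exchange. It stops All HMIOL Eyes at the 3 Month Visit.

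**Entry during the study.** Protocol 3.1 says that at the 3 Month Visit "subjects with satisfactory outcomes, or those opting not to pursue an optic exchange, will be entered into Cohort 1". For a subject with an acceptable outcome or no planned exchange, protocol 3.3.4 says "the subject will be entered into Cohort 1 and be followed at the 6 and 12 Month Visits prior to study completion". Protocol 8.3 then describes the pool: "The statistical summaries will be prepared for HMIOL Cohort 1, HMIOL Cohort 2, and HMIOL eye Cohort (Cohort 1 + Cohort 2").

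**Who can reach Cohort 2.** Protocol 3.2.4 bars the exchange where a finding or complication "is likely to increase complications with optic exchange procedure or present undue risk to the subject". Protocol 4.5 makes explantation a mandatory discontinuation, and 4.6 treats withdrawal after implantation as loss to follow-up.

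**The comparison.** SAP 5.4 lists adverse event rates against the ISO SPE rates for All HMIOL Eyes, Cohort 1 and Cohort 2. The method is an exact one-sided 95% lower bound at one year, and a cohort passes if the bound lies below the SPE rate. SAP 2 states that the SAP supersedes the protocol's analyses.

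**The concern.** Cohort 1 is defined by something that has not yet happened when its follow-up starts. An eye explanted, withdrawn or lost in the first three months has no exchange, so it belongs to Cohort 1 by definition. Cohort 2 eyes may have had adverse events before the exchange, but none that ended participation or led to exclusion under 3.2.4. Early device failures are therefore divided by the smaller Cohort 1 denominator, and Cohort 2's record is conditional on having reached the exchange. Each cohort's SPE result then partly reflects how eyes were assigned.

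The remedy would be to read the all-eyes result first. The SAP lists that comparison but closes the cohort at 3 months, nine months before the time point of the test. An analyst who needs a pooled one-year set must fall back on the protocol's sum of the two cohorts, and the protocol's own sections do not agree on whether early exits are in it. Early failures are among the most useful things a feasibility study can report to the confirmatory trial, so their denominator should be fixed in advance.

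**Working it through.** **The plan's own figure.** The plan gives no number for this point. The visible figure that rests on the pooled cohort is the power of 0.753 at n = 100 in protocol 8.1 (boundary 0.925, true value 0.85, one-sided 0.05). It reproduces: rejecting when 87 or fewer of 100 eyes succeed gives an exact alpha of 0.0364 and power of 0.7527. It is not in dispute. Protocol 8.1 specifies that test for all HMIOL eyes, taken after the exchange for Cohort 2, so the sizing also needs an all-eyes set beyond 3 months.

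**Inputs from the documents.** 105 enrolled and 44 exchanges (protocol 4.7.1, used here only as a plausible size), up to 200 subjects (protocol 3.1), and an SPE rate of 0.8% for secondary surgical intervention (SAP Table 1).

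**Assumptions.** Each subject contributes one implanted study eye. Early explants count as secondary surgical interventions, there are no others, and every implanted eye stays in the denominator. The visible text gives no early explant rate and does not say that an explant counts as such an intervention.

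**Effect on the rate.** With N implanted and E exchanged, x early explants give x/N in all eyes, x/(N − E) in Cohort 1 and 0/E in Cohort 2. Cohort 1's rate is N/(N − E) times the all-eyes rate: 105/61 = 1.72, or 200/156 = 1.28.

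**Effect on the test.** The exact lower bound L solves P(X ≥ x | n, L) = 0.05, so L is the 5% quantile of Beta(x, n − x + 1). The criterion is L < 0.8%.

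| N / E | x | All eyes: rate, L | Cohort 1: rate, L |
|---|---|---|---|
| 105 / 44 | 2 | 1.90%, 0.339%, pass | 3.28%, 0.586%, pass |
| 105 / 44 | 3 | 2.86%, 0.783%, pass | 4.92%, 1.354%, fail |
| 105 / 44 | 4 | 3.81%, 1.312%, fail | 6.56%, 2.271%, fail |
| 200 / 44 | 3 | 1.50%, 0.410%, pass | 1.92%, 0.526%, pass |
| 200 / 44 | 4 | 2.00%, 0.686%, pass | 2.56%, 0.880%, fail |
| 200 / 44 | 5 | 2.50%, 0.990%, fail | 3.21%, 1.271%, fail |

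These eyes contribute nothing to Cohort 2, where two events of any other origin would fail the same rate (2/44, L = 0.814%).

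**Other SPE rates at 105/44.** At 0.1% and at 0.3%, all eyes and Cohort 1 both fail from two events, so the verdicts do not split. At 3.0% (cumulative cystoid macular edema), Cohort 1 fails from five events and all eyes from seven. If every such eye stayed in Cohort 1, five or six events would split the verdict. Macular edema is one of the examples in protocol 3.2.4, but the exclusion is left to the investigator's judgment, so that is the extreme case.

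**The case against.** **The stronger reading.** A reader might infer from protocol 3.1, 3.3.4 and 8.3 that an eye leaving before the 3 Month Visit enters neither cohort and drops out of the pooled rate. Three early explants would then leave 0/102. The documents do not support this as the plan's rule. The synopsis sets out its cohort list for analysis, and its Cohort 1 has no 3 Month Visit condition, so Cohorts 1 and 2 together can equal all implanted eyes. Protocol 3.3.4 also treats Cohort 1 as the default when a planned exchange does not happen. The SAP, which supersedes, keeps early exits in both All HMIOL Eyes and Cohort 1. What stands is that the protocol's wording is inconsistent and should be reconciled.

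**No between-cohort test.** A reader might also infer that the plan attributes a safety difference between the cohorts to the exchange. The visible text plans no such comparison. Each cohort is set against the SPE rates, and post-exchange visits use the 3 Month Visit as baseline. Selection of Cohort 2 is inherent in an elective exchange and no definition removes it. This is right, and it is a reason to label the cohort tables and put the all-eyes result first.

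**The split is narrow.** At 105/44 against 0.8%, only three events separate all eyes from Cohort 1, and the all-eyes pass is by 0.017 percentage points. A subgroup of 61 and a pool of 105 will sometimes disagree. That is fair. The size of the effect is better read from the rate multiplier than from the pass or fail result.

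**Feasibility status.** SAP 4 disclaims definitive conclusions from the formal tests. That lowers the stakes but leaves the missing one-year all-eyes cohort unresolved.

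**Conclusion.** The concern holds in this form. Under the SAP, early failures and exits all fall on Cohort 1, Cohort 2 is free of them by construction, and the unselected cohort ends at 3 months although its SPE comparison is set at one year. For events in eyes that exit early, Cohort 1's observed rate is 1.72 times the all-eyes rate at 105/44 and 1.28 times at 200/44. A change of verdict against 0.8% is possible but confined to one event count in each case: three at 105/44 and four at 200/44. These figures rest on assumed event counts, on explants counting as secondary surgical interventions, and on 105/44 as the study size. The plan should be changed before analysis, but in a feasibility study without confirmatory claims this does not undermine the design.

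**What to change.** 1. In protocol 8.3 and SAP 4, define the pooled cohort as all eyes implanted with the HMIOL, including those that exit before the 3 Month Visit. Follow-up runs from Day 0 through 12 months, or through 12 months after the exchange for Cohort 2. This replaces the description as a sum of two cohorts and removes the 3-month limit for the SPE analysis.
2. Make this set the main SPE comparison in SAP 5.4.
3. State explicitly that Cohort 1 includes early exits.
4. Keep Cohort 1's 12-month cumulative table, but label it and the Cohort 2 table as selected by exchange status.
5. Add a split of events: before the 3 Month Visit for all implanted eyes, and after it by cohort.

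The split should supplement Cohort 1's cumulative table. Replacing that table with events after the 3 Month Visit alone would remove early failures from Cohort 1 and make it look safer.

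The cost is some additional tables and less weight on the separate cohort SPE results. The pool also mixes two clocks, 12 months from primary surgery and 12 months from the exchange, which protocol 8.3.1.1 already accepts. No new data are needed.
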